4.2 Intervention/Treatment procedures (by visits)

Effect of Menstrual Phase on Target Engagement

Transcranial Current Stimulation: Subjects will report for bilateral stimulation with tACS (one session) per menstrual phase, over the course of one menstrual cycle (unless it is an anovulatory cycle, in which case the participant will be asked to conduct the ovulation testing for one additional cycle). Each participant will receive tACS once in the follicular cycle phase and once in the luteal cycle phase, in counterbalanced order. The tACS stimulation will deliver a maximum amplitude of 2mA for a total of 40 minutes of stimulation per session. Electrodes will be saline soaked, 5x5cm, and placed over F3 and F4 locations to target dorsolateral prefrontal cortex. The return electrode will be located over CZ. A transcranial current stimulator designed by the [name] lab (XCSITE100 stimulator) will be used. After the first tACS session, participants will be instructed to begin daily mood ratings as recorded in the Daily Record of Severity of Problems via electronic Qualtrics survey. This 20-item self-report rating scale assesses physical and mood symptoms that accompany ovarian hormone changes and is often used as a dimensional measure of PMDD.

Electroencephalography (EEG): Each EEG session will last 8 minutes, and participants will alternate between having eyes open and closed at 2-minute intervals. A total of four EEG recordings will be performed throughout participation; two recordings per menstrual phase to be collected before and after stimulation. EEG will be recorded with a standard Nicolet v32 clinical EEG machine that is approved for clinical use and that has been used in all previous studies by the [name] Lab. Briefly, 10mm gold cup electrodes are fitted to the individual participants for brief, non-invasive recordings of brain activity.

4.3 Follow- up procedures (by visits): Will be scheduled only as necessary to assess acute suicidal ideation, severe mood deterioration, or severe somatic symptoms.

4.4 Unscheduled visits: not applicable

4.5 Concomitant Medication documentation: not applicable

4.6 Rescue medication administration (if applicable)

4.7 Subject Completion/ Withdrawal procedures: While extremely unlikely, any subject who becomes pregnant or who experiences a seizure during this study will be withdrawn. Any subject who experiences an acute worsening of mood or appearance of suicidal ideation will be assessed by the PI and may be withdrawn from the study. Subjects will be compensated monetarily for time and effort. For mileage subjects will be reimbursed 34 cents/mile. Compensation structure is as follows:

Participants will be paid \$40 per each tACS stimulation study visit, and an additional \$25 upon completion of the Daily Rating Forms. Total: \$105 per subject

Subjects will be paid at the end of their participation. If a subject is withdrawn by the investigators or withdraws herself, she will be compensated for participation up to the point of withdrawal.

- 4.8 Screen failure procedures:** As potential subjects will have been identified as appropriate through the related diagnostic screening protocol, we do not anticipate screening failures. In the case that a subject enrolls to participate in the trial but does not meet criteria, the study coordinator completing the screening process will clearly explain why the subject does not meet criteria. However, in the case that a subject does not qualify based on acute suicide risk, [name] will evaluate the subject and determine the appropriate clinical intervention.

5 STUDY EVALUATIONS AND MEASUREMENTS

- **List variables that will be abstracted from medical charts** – not applicable
- **Describe baseline evaluation** –
 - 1) Prior to enrollment in the tACS study, subjects must meet diagnostic criteria for PMDD. The DRSP (Daily Record of Severity of Problems), a validated daily symptom chart widely used for the diagnosis of PMDD, includes 21 items grouped into 11 domains that address the criterion of symptoms in PMDD (depression, anxiety, lability, anger, interest in activities, concentration, lethargy, appetite, sleep, control, and physical symptom). Each item is rated on a scale of 1 (“note at all”) to 6 (“extreme”). Using the DRSP, subjects must show symptom severity of 4 or greater for two days on a core emotional symptom in the luteal phase, absence of symptom severity during the follicular phase, and a 30% or greater increase in severity of symptoms in the 7 days preceding menses with 7 days following the end of menses.
 - 2) left prefrontal alpha power prior to tACS, obtained with EEG

Describe how measurements will be taken.

 - 1) symptom measures are self-reported on DRSP via Qualtrics survey tool; 2) EEG will be obtained for 8 minutes, with two-minute alternating intervals of eyes open and eyes closed.
- **Describe rating scales, tests, psychological tools, laboratory evaluations, etc.**
 - 1) Resting state EEG (RSEEG) recordings will be completed at several times during the course of the study. Subjects will complete an alternating eyes open/eyes closed RSEEG immediately before and after the 40 minutes of stimulation. This measure is used to determine the immediate after-effects of tACS on brain activity, specifically on alpha oscillation power, as well as how consecutive stimulation sessions may affect these after-effects.
 - 2) DRSP - Daily Record of Severity of Problems (DRSP) ratings daily throughout the study administered electronically via Qualtrics survey platform. This 20-item self-report rating scale assesses physical and mood symptoms that accompany ovarian hormone changes and is often used as a dimensional measure of PMDD.

5.1 Efficacy Evaluation (if applicable): Comparison of left prefrontal alpha power in post-tACS EEG compared with that preceding the procedure; comparison of degree of change in prefrontal alpha in follicular vs luteal phase.

6 STATISTICAL CONSIDERATION

This is repeated, single intervention (tACS) administered during the follicular and luteal phase. Change in left prefrontal alpha power on EEG is the primary outcomes. Effect of menstrual cycle phase is the secondary outcome. We plan to analyze our data using a repeated measure analysis of variance (ANOVA-R), with two within subject variables, each with two levels: time (pre vs post tACS), and menstrual cycle phase (follicular vs luteal). We will assess any effects of order of administration (follicular first vs luteal first) by including order as a between-subjects variable.

Clinical symptoms will be quantified as the mean of daily nighttime ratings (individual symptoms rated from 1 to 6) collected in the follicular (days 4 – 9) and luteal phases (the 6 days preceding menses) as recorded in the DRSP.

Decrease in left prefrontal power (reflection of reduction in alpha asymmetry) will be calculated by comparing results from the following time points: 1) immediately before the stimulation and 2) immediately following the stimulation in each of the follicular and luteal phases.

The main intent of this study is to conduct a pilot study, the results of which could be used in a larger trial that is appropriately powered for efficacy. Nonetheless, we intend to determine whether tACS influences alpha coherence on EEG. Due to the novelty of the application and the treatment strategy, we do not have all the required parameters to estimate the power for the repeated measure design on alpha coherence on EEG. However, the primary purpose is to demonstrate tACS associated changes in alpha coherence and whether that differs by cycle phase. The aim to demonstrate ‘target engagement’ does not necessarily lend itself to traditional power calculations and we will rely on [name] extensive experience with analyzing these data. In his experience, he is confident that if, in fact, if there are menstrual cycle differences in alpha coherence, 20 participants will be sufficient to demonstrate that effect.

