Study Phases Screening Study Treatment	
(1) Screening: Subjects with a diagnosis of PMDD confirmed by participation in a PMDD diagnostic study will be screened for eligibility in the tACS Study and review the informed consent forms. (2) Intervention: After consent is obtained, subjects will be asked to notify study personnel when they begin menstruating. If the subject is randomized to receive tACS in the follicular phase first, they will schedule a tACS session within 9 days of the onset of menses. If they are randomized to receive tACS in the luteal phase first, the subjects will then perform a home urine ovulation test every morning until they receive a positive result, at which point they will schedule their tACS session 9-13 days after the positive test result. Each stimulation session will last 40 minutes, plus the time it takes to place electrodes. EEG will be recorded before and after stimulation. At the end of the first session, subjects will be instructed to complete daily symptom rating scales for one completed menstrual cycle, or about 28-32 days. The second tACS session will be identical to the first, except it will occur in the opposite menstrual cycle phase as the first session.

Efficacy Evaluations	Primary efficacy measurement will be changes in left prefrontal alpha power or distribution (asymmetry) following tACS
Pharmacokinetic Evaluations	Not Applicable
Safety Evaluations	Primary measurements that will be used to assess safety:

-
- Subject semi-structured interview
 - Physical symptom items on the Daily Record of Severity of Problems (DRSP)
-

Statistical And Analytic Plan

We will use a t-test of pre-post changes to examine effects of tACS on left prefrontal alpha oscillations (primary outcome) and differences in effects as function of menstrual cycle phase (secondary outcome). There will be two levels of each of the two repeated within-subjects measures (pre vs post stimulation and follicular vs luteal phase). Order of administration will be assessed by considering order as a between- subjects variable.

DATA AND SAFETY MONITORING PLAN

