
1 BACKGROUND AND RATIONALE

Introduction

Premenstrual Dysphoric Disorder (PMDD) describes the cyclic appearance of affective symptoms and resultant impairment during the luteal phase of the menstrual cycle. The objective of the experiment is to determine if transcranial alternating current electrical stimulation (tACS) will alter prefrontal alpha oscillatory frequencies in women with PMDD, disruption of which has been implicated in other mood disorders. A secondary objective is to determine if menstrual cycle phase will influence the effects of tACS on alpha oscillations. Demonstration of 'target engagement' (alterations in left prefrontal alpha oscillatory frequencies with tACS) is a necessary first step before moving forward with subsequent research that would test whether tACS is a potential treatment for this disorder - promising research in other mood disorders suggests that it may be.

The cause of PMDD is unknown, the morbidity substantial, and the identified treatments limited in their effectiveness, since 40% of PMDD women are non-responders to SSRIs (Yonkers et al. 1997) and many additional women are intolerant of antidepressant induced side effects. PMDD is prevalent (6-8% of women of reproductive age), attended by substantial morbidity, and hence a significant public health problem. Indeed, by World Health Calculations, PMDD is associated with 4.5 million Disability Adjusted Life Years in the US alone (Halbreich et al. 2003). The rationale for testing whether tACS differentially alters target engagement in the follicular versus luteal phases of the menstrual cycle is described below.

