Brain stimulation by constant electric currents applied to the scalp (tDCs) modulates neuronal excitability in humans (Wagner, Valero-Cabre et al. 2007; Zaghi, Acar et al. 2010; Stagg and Nitsche 2011). Transcranial current stimulation with sine-wave stimulation waveforms (transcranial alternating current stimulation, tACS) likely enhances cortical oscillations in a frequency specific manner. The mechanisms of weak electric fields generated by tDCS and tACS previously have been demonstrated to interact with cortical network activity by altering the temporal activity structure of electric signaling in cortex ([name] and McCormick 2010; Ali, Sellers et al. 2013). In this study, we will assess whether tACS will decrease left frontal alpha power (8-12 Hz) and whether the extent of the decrease varies by menstrual cycle phase. An exploratory objective will be to examine the severity of the PMDD symptoms collected daily during the stimulation cycle and compare that severity with baseline symptoms ratings collected during the PMDD diagnostic study from which these participants will be recruited. The rationale for this stimulation is the known deficits in the overall structure of cortical activity in this frequency band in patients with mood disorders (Henriques and Davidson 1990; Baehr, Rosenfeld et al. 2004; Bruder, Sedoruk et al. 2008; Accortt, Stewart et al.

2011; Lin, Tsai et al. 2013) and the previously demonstrate clinical benefits of tDCS in the treatment of mood disorders (Berlim, Van den Eynde et al. 2013; Brunoni, Valiengo et al. 2013). In this study, we will use more targeted stimulation waveforms by employing bilateral tACS instead of tDCS. We hypothesize that this choice of a more sophisticated waveform that directly enhances synchronization between the two hemispheres may be more effective in engaging the target. tDCS modulates overall activity levels of the targeted cortical area in a non-specific manner. Here, however, we propose to evaluate a more specific stimulation modality, tACS, (10 Hz stimulation frequency) that has been shown to selectively enhance cortical alpha rhythms (Neuling et al. 2013). Since the selected patient population reportedly exhibits specific deficits in the alpha frequency band, our stimulation approach will provide a more targeted and therefore possibly a more effective manipulation.

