1.1 Non-Clinical and Clinical Study Findings

Potential Benefits: Research is designed to benefit society by gaining new knowledge. This study is not designed to benefit participants. Affective disorders are prevalent and representative an enormous public health burden. This study offers the general benefit of advancing our understanding of the brain circuitry that may be altered by the menstrual cycle in women with PMDD. In other ongoing studies, our results show enhanced alpha oscillations by tACS in patients with schizophrenia or depression, with associated decreased hallucinations in the former and depressive symptoms in the latter.

Risk/Benefit Assessment: Transcranial current stimulation has been used in hundreds of studies without any reports of serious side-effects (Brunoni and Amadera 2011). In our experience to date in studies of patients with schizophrenia and with depression, no serious adverse events have been reported. Therefore, transcranial current stimulation represents an extremely safe and non-invasive therapeutic approach.

Passing weak electric current through the scalp is also routinely done for measuring electrode resistance in all EEG recordings, a known safe procedure. Importantly, this stimulation mode has nothing to do with electroconvulsive therapy, which applies many orders of magnitude higher stimulation current. Rather, transcranial current stimulation is so weak that it does not produce super-threshold activation of neurons ([name] and McCormick 2010). There is a rare/theoretical likelihood that stimulation of neuronal circuits can lead to seizure. However, no studies have reported seizure as a side effect in recent trials of tDCS for depression or schizophrenia (Brunelin et al., 2012; Berlim et al. 2013) (nor in any trials to date). To further minimize this very small, theoretical likelihood of a seizure, we screen and exclude patients with personal and family history of neurological conditions from the study.

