2.1 Primary Objective

- 2.1.1 To determine whether a single session of tACS in women with PMDD decreases left prefrontal alpha power, ascertained by comparing EEG prior and subsequent to tACS.
- 2.1.2 To determine whether a single session of tACS will alter prefrontal alpha symmetry

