6.1 Primary Endpoint

Change in Alpha Frequency Electrical Activity in Left Frontal Cortex from Stimulation [Time Frame: 8-minute recording before vs after intervention]

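### Symmetry is a primary objective, but the analysis uses left-side alpha power only, so an equal fall on both sides would be read as reduced asymmetry

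*Combined protocol and SAP*

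**What the plan says.** **Objectives.** Objective 2.1.1 asks whether one session decreases left prefrontal alpha power. Objective 2.1.2, also primary, is: "To determine whether a single session of tACS will alter prefrontal alpha symmetry". The synopsis objective joins the two: lower left alpha, and by that route restore symmetry.

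**Efficacy measure.** Under Efficacy Evaluations the synopsis names "changes in left prefrontal alpha power or distribution (asymmetry) following tACS". Section 5.1 names left power only.

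**Endpoints and analysis.** Section 6 states: "Change in left prefrontal alpha power on EEG is the primary outcomes". Section 6.1 gives the primary endpoint as "Change in Alpha Frequency Electrical Activity in Left Frontal Cortex from Stimulation". Section 6.2 is the follicular-luteal difference in the effect on left alpha. Section 6.3 tests pre-post change in left alpha. Section 6 then says: "Decrease in left prefrontal power (reflection of reduction in alpha asymmetry) will be calculated by comparing results from the following time points". No right-side measure or left-right index appears in sections 5.1 or 6.

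**Target engagement.** Section 1 describes it without a direction: "alterations in left prefrontal alpha oscillatory frequencies with tACS) is a necessary first step before moving forward". The same section says of 10 Hz tACS "that has been shown to selectively enhance cortical alpha rhythms", and section 1.1 reports that "our results show enhanced alpha oscillations by tACS in patients with schizophrenia or depression".

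**Stimulation.** Sections 4.1 and 4.2 place electrodes over F3 and F4, with the return electrode over CZ.

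**The concern.** A primary objective has no endpoint or analysis attached. The parenthesis in section 6 fills the gap with an assumption: a left-side fall stands for reduced asymmetry only if the right side falls proportionally less. The plan does not check this, and stimulating both sides makes a right-side change plausible.

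Direction is a second, smaller gap. The objective is a decrease, but the endpoint is a change and target engagement is an alteration. No sidedness or success rule is stated. A rise is a live possibility on the protocol's own account of what 10 Hz stimulation does.

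At stake is what the pilot can hand on. The Protocol History in section 1 makes demonstrated engagement the condition for the intended follow-up study, and section 1 calls it a necessary first step. A reader of the results could be told that asymmetry fell when it was never measured.

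**Working it through.** **Inputs from the plan.** n = 20 (section 3.3); t-test of pre-post change in left alpha (section 6.3). The plan gives no SD, effect size, significance level or sidedness for this trial, so it has no figure of its own to reproduce on this point.

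**Assumed inputs.** Two-sided 5%; equal proportional fall on both sides of 20% or 15%; SD of the ln change 0.25 to 0.35; left-right correlation of the changes 0.3 to 0.8.

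**Step 1: what an equal fall does to asymmetry.** Index = ln(right) − ln(left). Take left 10 and right 8 in arbitrary units, with left higher as the rationale in section 1 describes.

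| Scenario | Left | Right | Index |
|---|---|---|---|
| Before | 10 | 8 | ln(8/10) = −0.223 |
| Both fall 20% | 8 | 6.4 | ln(6.4/8) = −0.223 |
| Left only falls 20% | 8 | 8 | 0 |
| Left only rises 20% | 12 | 8 | ln(8/12) = −0.405 |

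The second and third rows have the same left-side result. Left power alone cannot tell them apart.

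**Step 2: how often the left-only test is significant when asymmetry is unchanged.** Standardised change dz = |ln(1 − fall)| / SD; power from the noncentral t with 19 df and noncentrality dz × √20.

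| Fall, both sides | SD | dz | Left-only test significant |
|---|---|---|---|
| 20% | 0.25 | 0.223/0.25 = 0.893 | 96.6% |
| 20% | 0.35 | 0.223/0.35 = 0.638 | 77.2% |
| 15% | 0.25 | 0.1625/0.25 = 0.650 | 78.7% |
| 15% | 0.35 | 0.1625/0.35 = 0.464 | 50.4% |

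These do not depend on the right side or on the correlation. A test of the index in the same scenarios rejects in about 5% of trials, as it must when the true index change is zero.

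**Step 3: direction.** A two-sided test has the same power for a rise as for a fall of equal dz. At n = 20 that is 56% at dz 0.5 and 92% at dz 0.8.

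**Step 4: what a symmetry claim should require.** In simulation of the equal-fall scenarios at correlation 0.8, a significant left fall with an index point estimate merely in the right direction occurs in about 30% to 50% of trials. Requiring the index change itself to be significant toward symmetry brings this to about 2% to 3%.

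**Step 5: price of the second test.** For a true left-only fall (dz 0.5 to 0.8, correlation 0.3 to 0.8), both tests succeed in 34% to 93% of trials, against 56% to 93% for the left test alone.

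**The case against.** **The percentages are only the power of a paired t-test.** This stands. Rejecting is the correct result for the stated endpoint, and the 5% for the index follows from setting equal means. The figures show what the label in section 6 would do if both sides fell equally. They do not show how likely that is, and the documents do not predict it.

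**Asymmetry is not absent from the plan.** This stands in part. The synopsis efficacy measure and objective 2.1.2 both name it, so a reader who infers that the whole plan rests on left power alone goes too far; that describes sections 5.1 and 6. But the synopsis joins the two with 'or', which gives no order and lets left power suffice, and it does not supply the missing analysis.

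**An endpoint worded as a change beside a directional objective is ordinary two-sided practice.** This is fair, and it makes the direction point secondary. A reader might infer that a rise could be reported as restored symmetry. The documents do not support that: the synopsis objective, the Protocol History and section 6 all tie symmetry to a decrease. A rise could meet only the non-directional wording of section 6.1 and of target engagement in section 1.

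**There is no formal success rule, and this is a pilot.** Both are true. It is an inference that success would be judged on left power, and no decision threshold is defined for the follow-up study. That lowers the severity but does not give objective 2.1.2 an analysis.

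**Conclusion.** The point holds. Under sections 5.1 and 6 as written, objective 2.1.2 cannot be answered, and the parenthesis in section 6 would label an equal bilateral fall as reduced asymmetry. This follows from the definition of asymmetry and needs no numerical assumption. The size is illustrative: with a 20% fall on both sides and SD of ln change 0.25 to 0.35, about 97% to 77% of trials would give a significant left fall with no change in asymmetry (79% to 50% for a 15% fall). The falls, SDs and two-sided 5% level are assumptions.

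The lesser point is that the wording of the endpoint and of target engagement admits a rise that contradicts objective 2.1.1.

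Severity is should-fix: the trial is an open-label pilot, but this is the question it exists to answer.

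**What to change.** 1. In sections 6.1 and 6.3, keep change in ln left frontal alpha power as the primary endpoint, tested two-sided at 5%. Call it target engagement only if the 95% CI for the change lies wholly below zero. Report a rise as opposite to the hypothesis.
2. For objective 2.1.2, add pre-post change in ln(right) minus ln(left) frontal alpha from the same recordings, tested second in fixed sequence. Use one model for both, once the sponsor has reconciled the repeated-measures ANOVA in section 6 with the t-test in section 6.3.
3. Allow a claim of reduced asymmetry or restored symmetry only if the index change is significant in the direction of symmetry (95% CI excludes zero), not on a point estimate. With left alpha higher at baseline, that direction is a rise in the index toward zero; report the baseline index so this can be seen.
4. Replace the 'or' in the synopsis efficacy measure with this order, delete the parenthesis about asymmetry in section 6, and reconcile the statements in sections 6 and 6.4 that make alpha coherence the primary purpose.

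Cost: one derived variable from EEG already recorded, with no added visits or subjects and no loss of alpha under the fixed sequence. The real downside is that a symmetry claim needs a second test to succeed, so it is harder to make than from left power alone (step 5 of the working).
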